#### **10.3.8     Interim Analysis and Data Monitoring Committee**

An independent DMC composed of 3 physicians and a statistician not employed by the Sponsor will periodically review data from the study in planned meetings as described below.

Additionally, the DMC may, at its discretion, convene additional, unscheduled meetings at any time during the study.

**Initial Safety Review:** The DMC will review key safety data including the events of special interest specified in Section 11.10.2.2 after a vanguard cohort of at least 30 patients has had the opportunity to complete 4 weeks of treatment, and again after this cohort has had the opportunity to complete 12 weeks of treatment. Unless serious safety concerns have been observed, enrollment may continue while these reviews occur.

**Subsequent DMC Meetings to Review Safety:** The DMC will have another planned meeting to review safety when approximately 50% of the planned number of patients have been enrolled.

The DMC may also meet for unplanned meetings should safety observations during the study warrant such meetings.

**Additional Planned Interim Analysis of Key Safety and Efficacy Data:** an interim analysis of key safety and efficacy data may be conducted after approximately 50% of the planned number of patients enrolled and treated have had the opportunity to complete the 12-week double-blind, placebo-controlled treatment phase of the study to inform a decision regarding whether the study should stop for futility. To assess futility, the conditional power at the end of the study will be computed based on the data that are collected up to the interim analysis for the effect size of 0.34 that was used to calculate the power for the study. If the conditional power is less than 20%, the DMC may recommend stopping the study for futility. The conditional power will be calculated based on a two-sided t-test. The futility analysis may not occur if, for example, the study accrues quickly, as all or the large majority of patients may already be enrolled before approximately 50% of patients have finished the 12-week double-blind, placebo-controlled treatment phase.

The significance level associated with the primary and key secondary efficacy analyses will be adjusted based on the number of DMC meetings as described in the SAP.

## **11.0 SAFETY MONITORING AND RISK MANAGEMENT**

### **11.1 Safety Events and Reporting**

#### **11.1.1 Definitions**

Adverse Event (AE)	An AE is any unfavorable and/or unintended medical occurrence that presents during the course of the study (i.e., from the signature of informed consent through the Follow Up visit or earlier discontinuation, whichever comes first) regardless of its relationship to use of the investigational product. In studies of investigational products, no distinction is made between the investigational and control treatments with respect to AE reporting.
Serious AE (SAE) or Serious Suspected Adverse Reaction	Any AE or suspected adverse reaction that is deemed by the Sponsor or Investigator to have resulted in any of the following outcomes: death, a life-threatening AE (i.e., places the patient, in the opinion of the Sponsor or Investigator, at immediate risk of death from the reaction as it occurs), inpatient hospitalization or prolongation of existing hospitalization, a persistent or significant incapacity or disruption of the ability to conduct normal life functions, or a congenital anomaly/birth defect. Important medical events that may not result in death, be life-threatening, or require hospitalization may be considered an SAE when, based upon appropriate medical judgment, they may jeopardize the patient and/or require medical or surgical intervention to prevent one of the outcomes listed in this definition.

	Examples of such medical events include allergic bronchospasm requiring intensive treatment in an emergency room or at home, blood dyscrasias or convulsions that do not result in inpatient hospitalization, or the development of drug dependency or drug abuse.
Suspected Adverse Reaction	
An AE for which there is a reasonable possibility that the investigational product caused the AE. A “reasonable possibility” means there is evidence to suggest the investigational product is causally related to the AE. Examples include:
 
A single occurrence of an event that is uncommon and known to be strongly associated with an active ingredient or other component regardless of formulation;
 
One or more occurrences of an event that is not commonly associated with an active ingredient or other component, but is atypical in the study population;
 
The observation, when looking at data summaries, that a condition expected for the study population is occurring with increased frequency in comparison to concurrent or historical controls.

Treatment-Emergent AE (TEAE)	An AE that occurs after the patient has received the investigational product. AEs that occur during the Screening and Washout periods prior to treatment with the investigational product are not TEAEs.
Unexpected AE or Unexpected Suspected Adverse Reaction	Any AE or suspected adverse reaction not listed in the current Investigator’s Brochure (IB) or for which the specificity or severity of the event is not consistent with the IB; or, if an IB is not required or available, the specificity or severity of which is not consistent with the risk information described in the general investigational plan or elsewhere in the current application, as amended. For example, under this definition, hepatic necrosis would be unexpected (by virtue of greater severity) if the IB only referred to elevated hepatic enzymes or hepatitis.

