## **7.0 INVESTIGATIONAL PLAN**

### **7.1 Overall Study Design and Plan Description**

This is a randomized, double-blind, 2-arm, parallel group study of up to 274 evaluable patients designed to evaluate the safety and efficacy of ricolinostat for painful DPN.

After signing the ICF and agreeing to participate, initial eligibility assessments will be completed during a Screening visit scheduled between 45 and 14 days prior to planned randomization. Patients may continue one permitted medication for painful DPN if they have been taking it for at least 3 months prior to Screening, provided that the regimen and dose have been stable for at least 3 months prior to Screening and are expected to remain unchanged for the duration of the study. If any pain medication is stopped during the Screening period, then prior to proceeding to the Pain Observation Period:

1. The Investigator must document that there has not been a 'rebound flare,' or that if such a flare has occurred, it has resolved.
2. The Investigator must document that a steady state pain baseline is present.
3. A minimum period of time equal to at least 5 half-lives of the drug in question must pass.

Prior to randomization, patients will participate in a baseline Pain Observation period from Day -14 to Day -1, during which the NRS (average and worst pain) will be recorded daily using an electronic daily diary that will be completed by patients to allow patients to familiarize themselves with the pain rating procedures along with initiation of daily placebo dosing. During the Pain Observation period and thereafter during the study, patients will be allowed to use acetaminophen as rescue pain medication at a maximum dose of 500 mg at 6-hour intervals up to 4 times in any given 24-hour period. Patients will record the pain assessments and any rescue medication use. A follow-up phone contact will be conducted at Day -7 to Day -5 to review diary and dosing compliance.

At the end of the Pain Observation period, patients whose diary compliance, overall level of pain, and pain variability, along with placebo dosing meet entry criteria, will be randomized in a 1:1 ratio to receive either ricolinostat or placebo.

Pre-Treatment assessments will be completed as outlined in [Table 1](#). The first dose of study drug will be given in the clinic and a 12-lead ECG will be performed 1-hour post-dose.

[figure not shown]

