## 9.7 Follow-Up Period (Week 26 and Week 28)

Approximately 2 and 4 weeks after the last dose of study drug, study patients will have follow-up visits during which the assessments specified for those visits will be performed.

### 9.7.1 Week 26

The following procedures will be performed at Week 26:

- Administer C-SSRS (Since Last Visit version);
- Obtain vital signs (temperature, respiration rate, pulse, and blood pressure) while patient is sitting after a minimum 5-minute rest. Standing pulse and blood pressure to be obtained following sitting vital signs;
- Perform directed physical exam to assess changes from the prior visit or new concerns;
- Collect urine samples for the following:
  - Urine pregnancy test (if FOCBP);
  - Urine drug screen (performed at the discretion of the Investigator);

- Administer BPI-SF (pain interference section only);
- Administer NTSS-6;
- Perform UENS;
- Administer Norfolk Diabetic QOL-DN;
- Administer PGIC;
- Record concomitant medications and AEs;
- Instruct patient on daily completion of NRS (worst and average pain experienced each day) and rescue medication use, as applicable (at the discretion of the Investigator).

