#### **9.8 Premature Discontinuation**

If a patient is discontinued early from the study for any reason, the Investigator should make every effort to ensure that the final assessments at Week 24 are completed as outlined in the schedule of events. The reason for discontinuation will be recorded in the patient's record and the study database.

If the timing of the early termination is during the Safety Extension (Week 12 to Week 24), collection of the intraepidermal nerve biopsy should occur if patient previously provided consent and intraepidermal nerve biopsy collection occurred at Day 1.

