#### **Initial Reports**

All SAEs occurring from the time of first dose (start of Pain Observation period) of study drug until 30 days following the final dose of study drug must be reported to Medpace Clinical Safety

within 24 hours of the knowledge of the occurrence. After the 30-day reporting window, any SAE that the Investigator considers related to study drug must be reported to Medpace Clinical Safety or the Sponsor/designee.

To report the SAE, complete the SAE form electronically in the EDC system for the study. When the form is completed, Medpace Safety personnel will be notified electronically by the EDC system and will retrieve the form. If the event meets serious criteria and it is not possible to access the EDC system, send an e-mail to Medpace Safety at [[contact]](mailto:[contact]) or call the Medpace SAE reporting line (phone number listed below), and fax/e-mail the completed paper SAE form to Medpace (fax number listed below) within 24 hours of awareness. When the EDC system becomes available, the SAE information must be entered within 24 hours of the system becoming available.

Safety Contact Information: Medpace Clinical Safety

Medpace SAE reporting line – USA:

[contact], dial 3 or [contact], dial 3

[contact] or [contact]

E-mail: [[contact]](mailto:[contact])

Follow-Up Reports

The Investigator must continue to follow the patient until the SAE has subsided or until the condition becomes chronic in nature, stabilizes (in the case of persistent impairment), or the patient dies.

Within 24 hours of receipt of follow-up information, the Investigator must update the SAE form electronically in the EDC system for the study and submit any supporting documentation (eg, patient discharge summary or autopsy reports) to Medpace Clinical Safety via fax or e-mail. If it is not possible to access the EDC system, refer to the procedures outlined above for initial reporting of SAEs.

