##### 4.4.1. *Adverse events*

An adverse event (AE) is defined as any unfavorable and/or unintended medical occurrence that presents at any time from when the informed consent is signed through the final follow-up visit or earlier discontinuation (whichever comes first), regardless of relationship to the investigational product.

A *treatment-emergent adverse event* (TEAE) is any event that occurs after the start of study drug or was present at baseline and worsened after taking study drug.

*Serious adverse events* (SAE) are the subset of adverse events that are deemed by Regenacy or the Investigator to have resulted in any of the following: death, placing the patient at immediate risk of death, an inpatient hospitalization, a prolongation of existing hospitalization, a persistent or significant incapacity or disruption of the ability to conduct normal life functions, a congenital anomaly or birth defect, or an event that requires significant medical intervention to avoid those outcomes listed above.

*Suspected adverse reactions* are the subset of AEs for where this is a reasonable possibility that the investigational product caused the adverse event.

An *unexpected AE* is any suspected adverse reaction that is not listed in the current investigator's brochure (IB) or for which the severity is more extreme than what is listed in the IB; or is inconsistent with the general investigational plan or current application if the IB is not available.

*Events of special interest (ESI)*: The following events are defined to be of special interest: anemia, leukopenia, thrombocytopenia, renal impairment, congestive heart failure, and suicidality.

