#### 6.1.2. Analysis populations

The following populations are planned:

- Pre-randomized safety population (pSAF): All patients who have at least one observation during the pain observation period (day -14 to day -1/pre-treatment) and who were not randomized.
- Safety population (SAF): All patients who been randomized and received at least one dose of study drug
- Intent to treat (ITT) population: All patients randomized regardless of study drug administration
- Full analysis set (FAS) population: All patients who receive at least one dose of study drug, have a baseline average NRS score and, have at least one post-baseline average NRS score.
- Per-protocol population (PPP): All patients in the FAS population who have no major protocol violations, a valid baseline value of the NRS, meet all inclusion/exclusion criteria, missing no more than 2 weeks of diary data, and have a mean compliance rate of at least 60% (i.e., on average provide ratings on 4 or more days of each week).

6.1.3. *General considerations*

When presented, listings will be presented by patient number, treatment group, and measurement time.

In all analyses, the same number of decimal places as in the raw data will be presented for point estimates and univariate analysis. One more decimal place than in the raw data will be presented when reporting mean and standard deviation.

Continuous variables will be summarized by treatment group using descriptive statistics (n, mean, median, standard deviation, minimum, and maximum). For categorical variables, frequencies and percentages will be presented by treatment. The denominator for all categorical variables is the number of randomized patients.

All statistical testing will be based on a two-sided significance level of 0.05 unless otherwise stated.

*Baseline* is defined as the last observation prior to initiation of study medication.

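### The AE window closes at an undefined discontinuation while SAEs are reportable to 30 days after the last dose, follow-up visits for early leavers are unclear, and the start dates conflict

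*Protocol*

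**What the plan says.** **End of the window.** Protocol 11.1.1 (Definitions) limits an AE to the period "from the signature of informed consent through the Follow Up visit or earlier discontinuation, whichever comes first". SAP 4.4.1 has the same limit: "from when the informed consent is signed through the final follow-up visit or earlier discontinuation (whichever comes first". Both documents define SAEs as a subset of AEs. Protocol 11.1.2 has sites enter events that meet the AE definition. Protocol 11.1.3 (Initial Reports) sets a different window: "All SAEs occurring from the time of first dose (start of Pain Observation period) of study drug until 30 days following the final dose". Drug-related SAEs remain reportable after that, with no end date.

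**Early leavers.** Section 9.8 and the note under Table 1 say that "the Investigator should make every effort to ensure that the final assessments at Week 24 are completed as outlined in the schedule of events". Section 7.7 treats these as the patient's final evaluations. Section 9.7 says: "Approximately 2 and 4 weeks after the last dose of study drug, study patients will have follow-up visits". The Synopsis and Section 7.1 instead place those visits after the Safety Extension and time them from its last visit.

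**Start of the window.** AEs start at consent (Protocol 11.1.1, SAP 4.4.1). SAEs under Initial Reports start at the first placebo lead-in dose. The AE row of Table 1 starts at Day 1, and neither the Day -14 visit list (9.3.1) nor the Day -7 to -5 call (9.3.2) has an AE item. SAP Section 11 starts the safety analyses at randomization. SAP 6.1.2 nevertheless defines a pre-randomized safety population: "All patients who have at least one observation during the pain observation period (day -14 to day -1/pre-treatment) and who were not randomized".

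**The concern.** The AE and SAE windows should nest, because an SAE has to be an AE first. Here the wider category closes before the narrower one. A site that follows 11.1.1 and 11.1.2 to the letter stops entering new non-serious events once a patient discontinues, and has to report a late SAE that fails the AE definition.

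Patients who stop early include those who tolerate the drug poorly, so new events soon after their last dose are of interest. Completers have two scheduled visits after the last dose; whether early leavers have any is left to each site. AE ascertainment is then uneven between completers and early leavers, and between arms if discontinuation differs by arm.

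At the front end, events during analgesic washout and the placebo lead-in are AEs by definition but have no scheduled recording point. The protocol anticipates such events: Section 7.1 has the investigator document that there was no rebound flare, "or that if such a flare has occurred, it has resolved".

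**Working it through.** No sample-size or power figure bears on this point. The check is a comparison of the sections plus day arithmetic on the Table 1 windows.

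**Inputs.** Week 24 is Day 166 to 170 (target 168 in SAP Exhibit 4). Week 28 is Day 194 to 198 (target 196). Screening opens at Day -45. The lead-in starts at Day -14 and lasts 10 to 14 days. The SAE window closes 30 days after the last dose. I assume that a completer's last dose is on the day of the Week 24 visit.

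**1. Completers, end of window.**
- Week 24 to Week 28: 196 − 168 = 28 days, range 194 − 170 = 24 to 198 − 166 = 32.
- SAE window closes on Day 168 + 30 = 198, range 196 to 200.
- AE window closes at the Week 28 visit, so the nominal shortfall is 198 − 196 = 2 days, and at most 200 − 194 = 6 days.

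**2. Early leavers, end of window.** Take an illustrative last dose on Day 35. The SAE window closes on Day 35 + 30 = 65.
- Reading A: discontinuation falls on the day of the last dose and the 9.7 visits do not apply. The AE window closes on Day 35, a shortfall of 65 − 35 = 30 days for new events.
- Reading B: discontinuation means leaving the study, and the 9.7 visits run 2 and 4 weeks after the patient's own last dose. The AE window closes on about Day 35 + 28 = 63, a shortfall of 65 − 63 = 2 days.

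The text does not choose between them. Section 9.7 favors B, because it counts from the last dose and excludes nobody. Sections 9.8 and 7.7, the Table 1 note, the Synopsis and 7.1 favor A, because a patient who stops at Week 5 has no final Safety Extension visit to count from.

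**3. What depends on the reading.** A completer has Week 26 (vital signs, directed examination, AEs) and Week 28 (hematology, chemistry, skin check, AEs). An early leaver certainly has only the Week 24 set, which does include AEs, hematology, chemistry, ECG and skin check. A patient biopsied at early termination under 9.8 has no clearly stated later skin check.

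**4. Start of window.**
- Consent to first lead-in dose: up to 45 − 14 = 31 days inside the AE definition but outside the Initial Reports window.
- First lead-in dose to Day 1: 10 to 14 days inside both windows, with no scheduled AE item.
- Total before Day 1 without scheduled AE recording: up to 31 + 14 = 45 days.

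The SAP's pre-randomized safety population consists of patients who never reach randomization, so no AE assessment is scheduled for it.

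**5. Treatment-emergent status.** Protocol 10.3.7 and SAP 4.4.1 count events after the start of study drug. Initial Reports treats the lead-in placebo as study drug. Taken together, a lead-in event could count as treatment-emergent, although SAP Section 11 analyzes results only from randomization.

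**The case against.** The strongest reply is that the protocol does look after patients who stop, and much of it stands. A reader might infer from the AE definition that patients who stop for toxicity get no follow-up after their last dose. The documents do not support that:
- Section 11.1.2 makes the investigator follow every AE until it settles.
- Section 11.1.3 does the same for SAEs.
- Section 11.4 adds roughly weekly visits for clinically significant laboratory changes or unresolved treatment-emergent events.
- Sections 11.10.2.2 and 11.10.2.2.1 require follow-up after stopping for events of special interest.

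These rules follow events or abnormalities already found. None schedules a look for new ones, which is the part that remains.

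A reader might also take Reading A as settled, so that early leavers have no days and no visits after the last dose. It is one reading. Discontinuation is undefined, 9.7 can be read to include early leavers, and Table 1 of the SAP expects values after treatment discontinuation.

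Nor can one say that SAEs before the lead-in go unreported. The opening of 11.1.3 and Section 12.8 require immediate SAE reporting with no start date. The fault is that Initial Reports gives a later start than those two provisions. Section 11.1.2 likewise makes AE assessment the investigator's duty throughout the study, so pre-Day 1 events are not excluded; they lack a scheduled entry.

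Finally, completers' post-dose weeks follow open-label ricolinostat in both arms, so they give no randomized drug-versus-placebo contrast. That is correct, and it limits any claim about bias between arms.

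**Conclusion.** The point holds as a conflict of collection windows and an unclear instruction for early leavers. Followed literally, a stated rule drops new non-serious AEs after discontinuation and contradicts the SAE window. The AE window falls short by about 2 days for completers (at most 6), and by about 2 to 30 days for early leavers depending on the reading. At the front, up to 45 days have no scheduled AE entry.

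The documents give no discontinuation rate. At an assumed 15% to 25% of the 274 evaluable patients, 0.15 × 274 = 41 to 0.25 × 274 = 69 patients would be subject to the ambiguity. That counts all leavers, including those who withdraw consent and could not be followed under any wording. It is not a count of toxicity stops.

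A reader might infer that the comparison is biased toward making ricolinostat look safe. The documents do not establish this. Uneven ascertainment between arms arises only if discontinuation differs by arm, and its size would depend on that difference. The textual conflicts stand without any such assumption. This should be corrected; the cost is low.

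**What to change.** 1. Define discontinuation in Protocol 11.1.1 and SAP 4.4.1 as stopping study drug or leaving the study.
2. Use one AE and SAE data-collection window in 11.1.1, 11.1.3, Table 1 and SAP 4.4.1, so that AE collection is not shorter than SAE collection at either end. Delete the clause that closes the AE window at earlier discontinuation, or bring it into line with 11.1.3.
3. Reconcile 9.8, 7.7 and the Table 1 note with the Synopsis, 7.1 and 9.7, so that the protocol says whether the existing post-dose visits apply to early leavers and from which date they are counted. The clinical content of that follow-up is for the sponsor to decide.
4. Align the start in Initial Reports with the opening of 11.1.3 and with 12.8, and align the Table 1 AE row and the lists in 9.3.1 and 9.3.2 with the stated start. The pre-randomized safety population then has AE data to summarize.
5. State in Protocol 10.3.7 and SAP 4.4.1 that, for arm comparisons, the start of study drug means the first randomized dose, consistent with SAP Section 11.

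The cost is amendment and SAP wording, some eCRF visit mapping, and a short AE entry at the pre-Day 1 contacts. If the sponsor decides that the follow-up visits do cover early leavers, those visits are already designed. No analysis model or sample size changes.
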